De-identification and Data Transfer to ENRM VA: The PSG recordings in the data repository, comprised of electrophysiological measures (such as EEG, EOG, EMG) will be exported to a binary format and will be completely stripped of any identification marks and will be saved with coded filenames. A separate text file containing epoch by epoch (30 second duration) sleep stages will be also generated for each sleep study with no patient's identification inside the file nor as part of the filename. Other de-identified data includes a spreadsheet with demographic information and survey data from Table 1. The de-identified data will be transferred from Portland VA to ENRM VA via a shared network folder with limited access permission.

**Prospective Study I.** The retrospective study of the existing database is from clinical sleep studies where 6 EEG electrodes, covering the occipital, central, and frontal lobes of the two hemispheres, were used. This is because all sleep states can be scored by these limited number of electrodes. However, using these 6 EEGs limits the coherence analysis to general areas of the frontal, central, and occipital lobes and with no direct representation for other areas of the brain. The aim of this prospective study is to evaluate potential improvement on the performance of the Neuromarkers using a dense array (up to 64 channels) EEG montage that covers all areas of the scalp. In the control and PTSD subjects, we will perform sleep studies using a dense array EEG montage and will compare the performance of the Neuromarkers in distinguishing PTSD from non-PTSD groups.

This entails starting with the coherence analysis based on the six electrodes used in the preliminary study followed by evaluating the nominal improvement in discrimination ability (PTSD vs. absence of PTSD) with the use of extra channels. The control subjects will be recruited by

advertising in the Bedford VA common areas, and by distributing informational flyers via VA providers, Veteran organizations, and other Veteran networks (including Veteran Services Offices, Veteran Centers, CBOC's, and other programs). We may also place an advertisement on Craigslist. Eligible Veterans will be able to self-refer to be screened for the study. The PTSD group will be recruited from Veterans undergoing treatment of PTSD at ENRM VA before the start of their treatment (Veterans with PTSD recruitment described in Section 4.2.3).

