Depending on the outcome of this study and the amount of potential improvements that might be achieved using a denser EEG arrays, we will identify the exact montage to be used in the follow-up prospective study with PTSD patients undergoing psychotherapy. We will thus start with the 6-channel EEG of the standard clinical sleep study, and potentially expand it by including more EEG locations to presumably produce results that are superior (more precise) to those obtained in preliminary studies

**Prospective Study II.** Up to sixty (60) Veterans with PTSD symptoms undergoing treatment at the ENRM VA will be recruited by the Research Coordinator. The study protocol will be explained to potential subjects which will be given ample time to consider their participation in the study and ask any questions they may have. They may take it home with them if they need more time and then return to the PTSD clinic. If the Veteran agrees to participate, they will sign all informed consent documents and be given a copy to retain. All protocols and informed consents related to this project will be approved by the ENRM VA Institutional Review Board (IRB).

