For this analysis, the most promising  $PTSD_{dx}$  neuromarker identified in Hypothesis 1.1 (phase 2 development and validation analysis) will be prospectively evaluated in up to 25 PTSD and control subjects. First, a standardized effect size (mean difference / standard deviation) and corresponding 95% confidence interval will be calculated for the  $PTSD_{dx}$  neuromarker using the conventional 6- channel EEG approach. Then, using forward stepwise linear regression, extra EEG electrodes whose addition increases the model coefficient of determination ( $R^2$ ) by at least 1% will be included as candidate extra EEG channels. Once a final model is fit (with  $>6$  electrodes), the corresponding standardized effect size and 95% confidence interval will be calculated. Given the pilot nature and sample size for this analysis ( $n=25$ ), interpretation will not be based on formal statistical testing, but rather on the difference in the two effects sizes generated from the 6-channel EEG analysis vs. the  $>6$ -channel EEG analysis. Given that effect sizes can be interpreted as “small” (0.2), “medium” (0.5), or “large” ( $\geq 0.8$ ), we will use half of the width of adjacent categories (i.e. 0.15) to interpret meaningful improvement with the use of more than 6 EEG channels. For example, if the standardized effect size for the 6-channel EEG was 0.70, the  $>6$ -

channel EEG effect size would need to be  $\geq 0.85$  to indicate meaningful improvement and potential indication for a more complex EEG testing approach.

**Hypothesis 3:  $PTSD_{sev}$  will strongly correlate with the changes of PTSD symptoms and other measures of Quality of Health and Life as a result of psychotherapy.**

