## **4.0 Human Subjects**

### **4.1 General Characteristics**

The project has three groups of human subjects’ involvement:

1. A retrospective study, where the analyses will be applied to a large existing database of health-related and functional outcome measures, as well as sleep EEG recordings. Database contains sleep EEG recordings from Veterans with PTSD only (n=107), with TBI only (n=126), with both PTSD and TBI (n=87), with depression only (n=80), and controls (no PTSD/TBI/Depression; n=256. The inclusion of records from TBI and depression only groups is to provide training data for the biomarker to become maximally sensitive and specific to PTSD in the presence of co-morbidities such as depression and TBI.
2. Prospective study 1 with up to 25 PTSD and control PTSD (n=10) and control (n=10) where we will evaluate potential improvement on the performance of the biomarkers using a dense array (up to 64 channel) EEG montage. For each participant, we will perform 2 sets of sleep studies that will be at least one week apart.
3. Prospective study 2 in a cohort (n=60) of Veterans undergoing psychotherapy, where we will evaluate the sensitivity of biomarkers to the improvements in PTSD symptoms, and other functional and HRQoL measures, in response to psychotherapy. These participants will undergo sleep studies at four times of time (a) Within one week before initiation of their treatment protocol; (b) Within one week after their first therapy session; (c) at the conclusion of their treatment phase; and (d) About three months after their last therapy sessions

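### Hypothesis 2 judges the gain from extra EEG channels by a point difference in effect size that has no interval, and the two separate 95% intervals planned cannot supply one

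*Combined protocol and SAP*

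**What the plan says.** Section 3.5, Hypothesis 2, says that the best diagnostic marker from the retrospective study "will be prospectively evaluated in up to 25 PTSD and control subjects". An effect size with a 95% confidence interval is calculated for the 6-channel marker. Electrodes are then added by forward stepwise linear regression if they raise R² by at least 1%, and for the final model "the corresponding standardized effect size and 95% confidence interval will be calculated". The reading of the result is set out next: "interpretation will not be based on formal statistical testing, but rather on the difference in the two effects sizes generated from the 6-channel EEG analysis" and from the larger-montage analysis. A gain of 0.15 counts as meaningful, and the example is 0.70 against 0.85.

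Both effect sizes come from the same people. Section 3.3 (Prospective Study I) describes "starting with the coherence analysis based on the six electrodes used in the preliminary study followed by evaluating the nominal improvement in discrimination ability". It also says how the result will be used: depending on the outcome, "we will identify the exact montage to be used in the follow-up prospective study with PTSD patients undergoing psychotherapy".

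Section 4.1 gives the sample as "Prospective study 1 with up to 25 PTSD and control PTSD (n=10) and control (n=10", which adds to 20 and not 25. It also says: "For each participant, we will perform 2 sets of sleep studies that will be at least one week apart". The role of the two recordings in the montage comparison is not stated.

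**The concern.** The montage comparison turns on one number, the difference between two effect sizes, and that is the one number to which the plan attaches no measure of uncertainty. The variance of a difference between two estimates from the same people depends on their covariance. Neither marginal interval contains it, so a reader of the report could not reconstruct an interval for the gain.

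The larger-montage model is also selected and fitted in the same participants in whom its effect size is then measured, so its effect size is biased upward. A difference of 0.15 or more could be sampling noise, overfitting or a real gain, and the planned output could not separate them. That result would then inform the montage used in the treatment cohort.

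**Working it through.** **Inputs.** From the plan: up to 25 participants (section 3.5) or 10 + 10 (section 4.1), threshold 0.15, example 0.70 against 0.85, entry rule R² gain of at least 1%, up to 64 channels against 6. Assumed: a 12/13 split of 25; normal scores; within-group correlation r between the two scores from 0.5 to 0.98; 10 or 58 candidate extra channels (64 − 6 = 58).

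**1. The plan's own figures reproduce.** (0.5 − 0.2)/2 = (0.8 − 0.5)/2 = 0.15, and 0.70 + 0.15 = 0.85.

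**2. The two planned intervals in that example.** SE(d) = √(1/n₁ + 1/n₂ + d²/(2N)).
- 12/13, d = 0.70: √(0.1603 + 0.0098) = 0.412, interval −0.11 to 1.51. For d = 0.85: SE 0.418, interval 0.03 to 1.67.
- 10/10: −0.20 to 1.60 and −0.07 to 1.77.

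They overlap almost completely, and this says nothing about the precision of the gain.

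**3. An interval for the difference, two fixed markers.** With common d, SE = √(2(1 − r)(1/n₁ + 1/n₂) + d²(1 − r²)/N). For 12/13, d = 0.70, r = 0.8: √(0.0641 + 0.0071) = 0.267, half-width 1.96 × 0.267 = 0.52. The last two columns are simulated (8,000 runs per setting) with equal true d = 0.70 under both montages.

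| r | Half-width 12/13 | Half-width 10/10 | Difference ≥ 0.15 by chance, 12/13 | Same, 10/10 |
|---|---|---|---|---|
| 0.5 | 0.82 | 0.92 | 37% | 39% |
| 0.8 | 0.52 | 0.58 | 29% | 32% |
| 0.9 | 0.37 | 0.41 | 22% | 26% |
| 0.95 | 0.26 | 0.29 | 14% | 18% |
| 0.98 | 0.17 | 0.19 | 5% | 7% |

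Simulated SEs are about 5% to 13% larger than the formula gives, so these half-widths are if anything short. At every r shown the half-width exceeds 0.15. A result exactly at the threshold would therefore have an interval that includes 0; at r = 0.8 and 12/13 it is about 0.15 ± 0.52, or −0.37 to 0.67. With equal true d = 0.8 the chance figure is about 15% to 39% for r from 0.95 to 0.5.

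**4. With the planned stepwise selection.** True 6-channel d was 0.70, all extra channels were pure noise, inter-channel correlation was 0 or 0.8, and there were 400 runs per setting. The in-sample gain reached 0.15 in 74% to 100% of runs across all settings. The lowest figure was with 10 candidates and one channel added. With 58 candidates it was at least 91%. With no cap on the number of channels added, which is how the plan reads, it was 98% to 100%.

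**5. Whether a simple paired bootstrap is enough.** True d was 0.8, the extra channels were independent noise, and the final model was held fixed across resamples. The rule tested was a difference of at least 0.15 with a paired interval excluding 0. It still declared improvement in up to 9% of runs (10 candidates, 1 added), about 23% to 49% (10 candidates with 3 added, or 58 with 1 added), and 98% to 100% (58 candidates, 3 added). Resampling has to repeat the selection and score the model out of sample.

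**The case against.** The strongest reply is that this is a declared pilot. The plan gives the sample size as its reason for not testing, speaks only of a potential indication for a more complex montage, and words the expansion for the later study conditionally. All of that stands. Omitting a formal test is a disclosed choice and not an error. An interval is not a test, however, and the plan already reports 95% intervals; they are attached to the two components and not to the gain that is interpreted.

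A reader might infer that the plan treats paired data as two independent samples, so that its intervals are far too wide for the comparison. The documents do not support that. The point difference is already within-participant, and nothing tells the reader to combine the two intervals or compare them for overlap. Each describes its own effect size properly, apart from selection bias in the second. What is missing is an interval for the difference.

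It is also fair that the chance figures depend on an unstated correlation. The 6-channel marker is contained in the larger model, so r may be high, and for fixed markers at r = 0.98 the chance of reaching 0.15 falls to 5% to 7%. The two recordings per participant could change the variances too. The selection result in step 4 does not depend on r in that way.

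**Conclusion.** The concern holds in this form: the quantity that informs the Study 3 montage has no interval, the two planned intervals cannot provide one, and the 0.15 rule applied to the in-sample point difference can easily be met without any true gain. For two fixed markers that happens in about 15% to 39% of studies (equal true d = 0.8, r from 0.95 to 0.5, groups of 10/10 or 12/13). With in-sample selection of noise channels it happens in nearly all simulated studies unless few candidates are offered and only one is added.

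The sizes rest on normal scores, the assumed r, the 12/13 split and a simple noise structure for the extra channels. The absence of the interval rests on none of these. It should be corrected before the montage is chosen. It does not call for a larger study, and it does not show that the dense array fails to help.

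**What to change.** In section 3.5, Hypothesis 2, make one 95% interval for the within-participant difference in effect size the basis for interpretation:

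- Resample whole participants within each group.
- In each resample, repeat the stepwise channel selection and model fit.
- Score the larger model only on participants not used to select or fit it, for example by out-of-bag or cross-validated scores. Keep copies of the same participant out of both training and test sets, and compute the 6-channel effect size in the same held-out participants.
- Keep 0.15 as the size threshold, applied to the out-of-sample difference, and report it with this interval.
- If the interval includes 0, describe the gain as unresolved and the Study 3 montage as a working choice.

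Call the interval approximate: for fixed markers, percentile-bootstrap coverage in simulation was about 90% to 93%. The same edit should reconcile 25 with 10 + 10 and say how the two recordings per participant enter the comparison.

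The cost is a few sentences and a short script, with no new data or participants. The downside is that at this sample size the gain will often be reported as unresolved, even where it is real.

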## **2.2 Preliminary Studies**

In preliminary studies on EEG acquired during sleep from Veterans with PTSD alone (n=38), TBI alone (n=30), PTSD and TBI (n=25), and an aged matched no PTSD or TBI control group (n=38), we have shown that a set of neuromarkers were highly sensitive/specific to the presence of PTSD, and highly sensitive to the severity of symptoms in PTSD group.

The PTSD neuromarkers of this project are built from combination of regional brain coherence markers (BCM). BCM computation is based on the levels of coherence and synchronicity between pairs of scalp EEG activity. These coherence values were computed for the entire sleep study using

5-second sliding windows that were overlapped by 1 second. The frequency band spanned from 0.2 Hz to 50 Hz with a resolution of 0.2 Hz. Vectors of BCM were constructed over each of the five stages of sleep study (Awake [W], Rapid Eye Movement [REM], non-REM [NREM] stages N1, N2, and N3). Our analysis showed that the markers computed in awake and stage N2 sleep were significantly different in PTSD than the control group and also produced the highest level of correlation with the PTSD symptom.

The following figure shows the excellent capability of the PTSD diagnostic Neuromarker ( $PTSD_{dx}$ ) and PTSD severity marker ( $PTSD_{sev}$ ) in differentiating Controls from PTSD, and in correlation with symptoms, respectively.

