### 3.5 Analysis Plan

#### **Hypothesis 1.1 $PTSD_{dx}$ will discriminate PTSD patients from control subjects without PTSD;**

The primary evaluations will be based on computation of  $PTSD_{dx}$  and  $PTSD_{sev}$  markers similar to the approach used in preliminary studies. This will occur in multiple phases, all of which will randomly divide and analyze the full sample of 656 veterans into 3 groups of 219, 219, and 218 subjects, and in proportion to the presenting symptom/condition status of veterans, as follows:

Condition (Group)	Total N	Subsample		
		Sample 1	Sample 2	Sample 3
PTSD only (group A)	107	36	36	35
TBI only (group B)	126	42	42	42
PTSD & TBI (group C)	87	29	29	29
Depression only (group D)	80	26	27	27
Controls (no PTSD, TBI, depression) (group E)	256	86	85	85

To test our first hypothesis and in the first phase of analysis, we will use the specific  $PTSD_{dx}$  neuromarker previously identified in our preliminary study of 76 veterans, and evaluate it separately in all 3 subsamples. Analysis of covariance (ANCOVA) will be used to compare adjusted mean  $PTSD_{dx}$  scores between the PTSD only group (Group A) vs. planned contrasts with the remaining 4 groups. The a-priori-defined contrasts will consist of the following 5 comparisons: A vs. E, A vs. B/C/D combined, A vs. B, A vs. C, and A vs. D. Thus, for each subsample, there will be 5 planned comparisons, and hence a total of 15 comparisons. We expect the largest differences in mean  $PTSD_{dx}$  scores between PTSD only (group A) and controls (Group E), but nonetheless, also expect the PTSD only group to have higher mean  $PTSD_{dx}$  scores than Groups B, C, and D.

In these analyses, models will be adjusted for potential confounding variables (e.g. current use of sleep medications) identified by use of student *t*-tests (or Wilcoxon tests) for continuous variables and chi-square tests for categorical variables. Given the 5 planned comparisons for each subsample, a modified p-value of 0.01 will be used to define statistical significance. While arbitrary, “validation” of the previously identified  $PTSD_{dx}$  neuromarker will be based on statistical significance as follows: (i) all 3 comparisons of Group A vs. Group B at  $p<0.01$ , AND at least 9 of the 12 remaining comparisons at  $p<0.01$ .

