In the second phase of this hypothesis, the approach used to identify the most promising  $PTSD_{dx}$  neuromarker described in Preliminary Studies will be applied to the much larger dataset of 656 veterans. For this analysis, Subsamples 1 and 2 will serve as training (development) samples, and Subsample 3 will serve as the validation sample. For subsample 1, ANCOVA will again be used to identify the 5 most promising  $PTSD_{dx}$  neuromarkers (based on corresponding *F* and *p*-values) rank ordered across the 5 planned comparisons described above. This process will be repeated for Subsample 2. From these results, the most promising  $PTSD_{dx}$  neuromarker will be selected based on the lowest aggregate rank scores across both subsamples and across all 5 planned comparisons. Once this  $PTSD_{dx}$  neuromarker is identified, it will be formally tested using the 5 defined planned comparisons within Subsample 3, and again using a *p*-value of  $<0.01$  to define statistical significance. In aggregate, these analyses will determine whether the originally identified  $PTSD_{dx}$  neuromarker can discriminate between veterans with and without PTSD, and whether a potentially

more promising  $PTSD_{dx}$  neuromarker is identified.

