**Hypothesis 1.2:  $PTSD_{sev}$  will strongly correlate with PTSD symptom severity level**

Using the same database as in retrospective study and focusing only on PTSD subjects, an analogous approach to that described for hypothesis 1.1 will be used. The principal difference will be that the independent variable,  $PTSD_{sev}$ , is a continuous variable rather than a categorical variable. Therefore, multiple linear regression will be used with  $PTSD_{sev}$  as the independent variable, and the PCL-5 symptom severity scale as the dependent variable acquired on the day of the sleep study. We will also examine the correlation of  $PTSD_{sev}$  with the other measures of quality of health and life in the database, particularly RQP (Rivermead Post-Concussive Symptom Questionnaire), PHQ-9 (Patient Health Questionnaire), FOSQ (Functional Outcome of Sleep Quality), ISI (Insomnia Severity Index), and Promis-29. The results of these analyses will provide a comprehensive examination of this hypothesis with respect to how accurately  $PTSD_{sev}$  can determine the severity of PTSD, and how well it is correlated with quality of life measures.

**Hypothesis 2: Use of a dense array (up to 64 channel) EEG montage, as compared to 6-channel EEG, will improve discrimination of PTSD patients from control subjects without PTSD.**

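### Hypothesis 2 compares a 6-channel marker carried over from Study 1 with a >6-channel model selected and fitted on the Study 2 subjects, so the 0.15 gain rule mixes fitting gain with any benefit of extra electrodes

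*Combined protocol and SAP*

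**What the plan says.** Section 3.5 states Hypothesis 2 as: "Use of a dense array (up to 64 channel) EEG montage, as compared to 6-channel EEG, will improve discrimination of PTSD patients" from controls. Its analysis paragraph has three steps.

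- **Six channels.** The leading PTSDdx marker from the second phase of Hypothesis 1.1 "will be prospectively evaluated in up to 25 PTSD and control subjects". A standardized effect size is calculated for that "neuromarker using the conventional 6- channel EEG approach". No re-estimation on Study 2 data is described.
- **More than six channels.** "Then, using forward stepwise linear regression, extra EEG electrodes whose addition increases the model coefficient of determination" by at least 1% are brought in. A final model is fitted and its effect size is calculated in the same subjects. No cross-validation, hold-out or optimism correction is mentioned.
- **Decision.** Interpretation rests not on a test but "rather on the difference in the two effects sizes generated from the 6-channel EEG analysis" and from the larger model. A gain of 0.15 counts as meaningful, for example 0.70 rising to 0.85.

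The Study 1 marker is chosen by the "lowest aggregate rank scores across both subsamples and across all 5 planned comparisons". Those comparisons are "A vs. E, A vs. B/C/D combined, A vs. B, A vs. C, and A vs. D", where A is PTSD only and E is controls.

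Under Prospective Study I in Section 3.3, the result feeds the choice of montage for the follow-up study. The sample is up to 25 in Sections 3.2 and 3.5. Section 4.1 also gives 10 plus 10.

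**The concern.** Hypothesis 2 is about electrodes. The two sides of the comparison differ in electrode count and also in whether the score was fitted to these recordings. One side is an externally chosen score. The other is optimised on the people used to evaluate it. A gain of 0.15 can then arise from fitting alone and be credited to the dense array. Because the point difference is itself the decision rule, the bias carries directly into the montage decision for the next study.

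**Working it through.** **1. The plan's threshold.** Half the distance between adjacent effect-size categories is (0.5 − 0.2)/2 = (0.8 − 0.5)/2 = 0.15, and 0.70 + 0.15 = 0.85. Both figures reproduce. The plan gives no sample-size calculation for Study 2.

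**2. How small a rise in R² passes.** In a two-group linear regression, d² = [R²/(1 − R²)] × (N − 2) × (1/n1 + 1/n2). For an assumed 12/13 split the multiplier is 23 × (1/12 + 1/13) = 3.686.
- d = 0.70: 0.49/3.686 = 0.133, so R² = 0.133/1.133 = 0.117.
- d = 0.85: 0.7225/3.686 = 0.196, so R² = 0.196/1.196 = 0.164.

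A rise of 0.047 is enough. In-sample R² cannot fall when a channel is added, so the fitted effect size cannot fall either.

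**3. Extra channels that are pure noise.** Assumptions: true six-channel d = 0.70; the marker enters as one score; extra channels are independent noise; the 1% rule is an in-sample R² rise of 0.01; the regression outcome, which the plan does not name, is PTSD status. There were 1,000 simulated studies per row. Up to 64 channels leaves 64 − 6 = 58 extra.

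| Extra candidates | 12/13: median gain (share reaching 0.15) | 10/10: median gain (share) |
|---|---|---|
| 1 | 0.07 (33%) | 0.10 (41%) |
| 2 | 0.20 (59%) | 0.24 (65%) |
| 6 | 0.67 (97%) | 0.88 (98%) |
| Best 1 of 58 | 0.71 (100%) | 0.91 (100%) |

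**4. Re-weighting the six channels, with no extra electrode.** The plan does not say whether the marker enters as one score or as separate features. As one score, re-fitting it alone leaves the size of d unchanged. As 2, 3 or 6 separate features at 12/13, re-fitting gives median gains of 0.07, 0.20 and 0.56, and 0.15 is reached in 34%, 60% and 96% of 3,000 runs. This holds even when the carried-over weights are already optimal.

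**5. The part that cross-validation would leave.** Suppose a second six-channel feature, unused by the marker, has effect size d2 and correlation r with it. Suppose also that the extra electrodes are only noisy copies of that feature. The population effect size of the best linear score is √(d′R⁻¹d), where R is the correlation matrix. With d2 = 0.60, r = 0 and one copy correlated 0.9 with the feature:
- planned comparison: √(0.49 + 0.54²) = √0.7816 = 0.884, a gain of 0.184;
- six channels re-fitted with the feature: √(0.49 + 0.36) = 0.922, to which the copy adds 0.00.

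The grid was d2 = 0.46, 0.50, 0.60, 0.70; r = 0, 0.2, 0.3; and one copy at 0.9, or two or five at 0.8, giving 4 × 3 × 3 = 36 cells. The low end, 0.46, is the smallest observed effect giving p<0.05 in a 38 versus 38 comparison, the group sizes in Section 2.2. The gain runs from 0.04 to 0.26. It reaches 0.15 in 10 of the 36 cells and in none with d2 of 0.50 or less (maximum 0.145). At r = 0.5 it is 0.01 to 0.10, and at r = 0.6 it is 0.00 to 0.07.

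**6. Changing only the comparator.** With stepwise selection over six candidates (two copies and four noise channels, d2 = 0.60, r = 0), the rule is met in about 97 to 99% of studies as planned. With an in-sample like-for-like comparator it is met in about 94 to 97%.

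**7. Same procedure on both sides, scored out of sample.** With leave-one-out, selection repeated inside the loop, 12/13 and noise-only extra channels (200 runs per setting), the median difference is −0.19 to +0.08. Chance passes of 0.15 still occur in about 29 to 48% of runs.

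**The case against.** A reader might infer that the carried-over marker is so handicapped as a comparator that it drives the result by itself at any sample size, leaving Study 2 unable to answer its question. The documents do not support that, for four reasons.

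- That the marker is frozen is an inference from the absence of a re-fit step. Section 3.3 speaks of beginning with coherence analysis of the preliminary study's six electrodes, which could mean a fitted six-electrode base model. The two sections need reconciling.
- The contrast mismatch is partial. PTSD only versus controls is one of the five contrasts and is expected to be the largest. Section 4.1 gives a reason for including the TBI and depression records: specificity amid co-morbidity.
- Unused six-channel information is assumed. Section 2.2 reports that "the markers computed in awake and stage N2 sleep were significantly different in PTSD than the control group". It also says the markers combine regional measures, and it does not show that either state adds signal beyond the chosen marker. Features from the same head and night may well correlate above 0.3, which shrinks the gain.
- At 20 to 25 subjects, in-sample selection already forces most passes, so changing the comparator alone barely alters the decision (step 6).

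These points limit the size of the persistent part. They do not make the two effect sizes comparable. Nor does the pilot label, since the untested point difference is what decides.

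**Conclusion.** The concern holds in limited form. As written, the difference judged against 0.15 contains a fitting gain as well as any gain from extra electrodes, and the rule can be met with no new information in those electrodes. At 20 to 25 subjects most of the excess is in-sample selection and fitting. The further part, from six-channel information the marker does not use, would remain under cross-validation, but the documents do not allow it to be sized. The range of 0.04 to 0.26 applies only if an unused feature with d of 0.46 to 0.70 and correlation of 0 to 0.3 exists, and the gain is smaller at higher correlation. The direction does not depend on the simulation assumptions. The sizes do: a true d of 0.70 (the plan's example), independent noise channels, the number of candidates, and PTSD status as the regression outcome.

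**What to change.** In the Hypothesis 2 paragraph of Section 3.5:

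1. Keep the carried-over marker's effect size as a descriptive result.
2. Run the same regression and selection rule twice on Study 2 data: once with a small pre-specified set of coherence features from the original six electrodes, and once with the extra electrodes also allowed.
3. Score both by cross-validation, repeating selection inside each fold.
4. Apply the 0.15 criterion to the difference between these two out-of-sample effect sizes, and report it with an interval.
5. State the regression outcome and how the marker enters the model, and align the baseline with Section 3.3.

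The six-electrode set must be small. Fifteen electrode pairs, about 250 frequency bins (50/0.2) and five stages give 15 × 250 × 5 = 18,750 possible features, and an unrestricted re-fit in 20 to 25 people would saturate.

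The cost is some rewording, the choice of the feature set, and extra model runs on recordings already planned. The apparent dense-array gain will usually be smaller. The fix removes the systematic bias but not the imprecision: given chance passes of about 29 to 48%, the result should be read as indicative only.
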